12.4. REPORTING OF ADVERSE EVENTS

Investigators will notify the sponsor of any unexpected or serious adverse events, whether related or not related to the studied device. If the adverse event is reportable, the manufacturer will report the event in accordance with applicable regulations.

13. PREPARATION AND STORAGE

13.1. STORAGE AND HANDLING

The Pocket-X Gel will be stored in accordance with manufacturer instructions between 20°C - 25°C, away from direct heat and sunlight.

13.2. PREPARATION

Prior to treatment, the device will be prepared for application according to manufacturer instructions:

–the Pocket-X Gel pre-filled syringe will be removed from its packaging, its cover will be removed, and one of the 2 tips provided with the device will be attached to the syringe.

14. REGULATORY AND ETHICAL CONSIDERATIONS

14.1. INFORMED CONSENT

A signed informed consent form must be obtained from each participant prior to enrollment. The informed consent will provide details of the study, the studied device and the intervention and procedures the participant will undergo as part of the study.

Participants will have the opportunity to carefully review the written consent form and ask questions prior to signing. The participant will sign the informed consent document prior to initiation of any study procedure. Participants must be informed that participation is voluntary and that they may withdraw from the study at any time.

The informed consent will be approved by the study's ethics committee prior to initiation of participants screening.

14.2. STUDY DISCONTINUATION AND CLOSURE

This study may be temporarily suspended or prematurely terminated if there is sufficient reasonable cause. If the study is prematurely terminated or suspended, the investigators will promptly inform study participants, the ethics committee and sponsor and will provide the reason(s) for the termination or suspension.

Circumstances that may warrant termination or suspension include, but are not limited to:

- Determination of unexpected, significant, or unacceptable risk to participants
- Insufficient compliance to protocol requirements
- Data that is not sufficiently complete and/or evaluable
- Determination of futility

Study may resume once concerns about safety, protocol compliance, and data quality are addressed, and satisfy the sponsor and ethics committee.

14.3. PARTICIPANTS CONFIDENTIALITY

Participants confidentiality and privacy will be strictly held in trust by the participating investigators, their staff, and the study's sponsor.

All study procedures will be conducted in as private setting as possible.

The study participants identifying information (i.e. full name and/or ID number) and contact information will be securely stored at the clinical site for internal use during the study.

The participants study data will be available to the sponsor for the purpose of monitoring, statistical analysis, safety evaluation, scientific reporting and regulatory obligations. This will not include the participant's contact or identifying information. Rather, individual participants and their research data will be identified by a unique study identification number and the participant's initials.

15. STATISTICAL ANALYSIS

15.1. SAMPLE SIZE CONSIDERATION

The rationale for sample size was based on demonstrating a difference in change in pocket depth between the tested segments and the control, reflecting effect size of 0.5 with 80% power and 5% significance level.

Effect size is defined as the difference in change between the treatments adjusted to standard deviation, and calculated as follows:

$$\frac{(\text{Change from baseline in Test segments} - \text{Change from baseline in Control segments})}{\text{Common standard deviation of the change}}$$

Sample size Justification *

A sample size of 27 will have 80% power to detect an effect size of 0.5 using a Paired t-test with a 0.05 one-sided significance level.

Assuming ~20% dropout rate, 34 subjects will be recruited, in order to have 27 participants who complete the study.

Reference:

* Additional sample size justification presents the same sample size and effect size, but specifies the expected changes within each treatment and the common standard deviation:

A sample size of 27 will have 80% power to detect a difference in means of -0.5 (e.g. a First condition mean, μ_1 , of 2.0 and a Second condition mean, μ_2 , of 2.5), assuming a standard deviation of differences of 1.0, using a paired T-test with a 0.05 one-sided significance level.

The calculations are summarized in the table below:

	1	2
Test significance level, α	0.05	0.05
1 or 2 sided test?	1	1
First condition mean, μ_1	2.0	
Second condition mean, μ_2	2.5	
Mean difference, $\mu_d = \mu_1 - \mu_2$	-0.5	
Standard deviation of differences, σ_d	1.0	
Effect size, $\delta = \mu_d / \sigma_d$	0.5	0.5
Power (%)	80	80
N	27	27

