15.2. STATISTICAL METHODS

Study Population:

Intent-to-treat (ITT) population – all patients enrolled to the study who received at least one treatment.

Per Protocol (PP) population - all patients in the ITT population who completed the study according to the protocol and with no major protocol violations.

General

All measured variables and derived parameters will be listed individually and, if appropriate, tabulated by descriptive statistics. For categorical variables, summary tables will be provided giving sample size, absolute and relative frequency and 95% CI (Confidence Interval) for proportions by study arm. For continuous variables, summary tables will be provided giving sample size, arithmetic mean, standard deviation, median, minimum and maximum and 95% CI (Confidence Interval) by study arm for means of variables.

All tests will be two-tailed, and a p-value of 5% or less will be considered statistically significant.

The data will be analyzed using the SAS ® version 9.3 (SAS Institute, Cary North Carolina).

Periodontal pockets treated with Pocket-X Gel will be analyzed vs.control pockets.

Efficacy assessment

The following efficacy parameters will be summarized in appropriate tables by treatment and visit. Changes from baseline will be summarized as well.

- Pocket probing depth
- Bleeding index
- Recession level
- Clinical attachment level
- Mobility grade
- Furcation
- Specific periodontal bacteria quantification [optional]

The Paired T-test or Signed rank test for two means (paired observations) (as is appropriate) will be applied for analyzing the calculated changes by time point within each treatment.

The Paired T-test or Signed rank test for two means (paired observations) (as is appropriate) will be applied for analyzing the difference in the above measurements and changes between the treatments.

Responder will be defined based on improvement of gingival healing and natural sealing of periodontal pockets. Chi-square test or Fisher's Exact test (as is appropriate) will be applied for comparing the proportion of responders between the tested and the control segments.

The efficacy results will be compared also to literature data, if available. The two-sample T-test or Non-parametric Wilcoxon-Mann-Whitney Rank sum test for independent samples (as is appropriate) will be applied for comparative analysis.

Safety assessment

Safety assessments will be based on Adverse Events (AEs) and oral inspections recorded at each visit.

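### The sample size rests on a one-sided 5% test, but every analysis is to be two-tailed at 5%; with the planned 27 completers the stated 80% power is about 71%

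*Combined protocol and SAP*

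**What the plan says.** Section 15.1 opens by describing the target as a difference in change in pocket depth, "reflecting effect size of 0.5 with 80% power and 5% significance level", without saying whether the test is one- or two-sided. The justification that follows does say: "A sample size of 27 will have 80% power to detect an effect size of 0.5 using a Paired t-test with a 0.05 one-sided". A second justification with explicit means gives the same N, "assuming a standard deviation of differences of 1.0", again at a one-sided 0.05 level. The table row "1 or 2 sided test" shows 1 in both columns. Allowing for about 20% dropout, 34 participants are recruited so that 27 complete.

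Section 15.2, under General, states: "All tests will be two-tailed, and a p-value of 5% or less will be considered statistically significant". The paired t-test or signed rank test "will be applied for analyzing the difference in the above measurements and changes between the treatments". That covers the pocket-depth comparison, and nothing exempts it from the two-tailed rule.

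Section 15.1 also gives a formula for the effect size. Its denominator is "Common standard deviation of the change", whereas the table divides by the standard deviation of the differences.

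**The concern.** Sample size and analysis should refer to the same test. Here the sample size assumes that all 5% of the type I error lies in the favourable direction, while the analysis splits it between two tails. The two-tailed test has a higher critical value, so its power at the same N is lower than stated.

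Two things are at stake. First, a null result would be judged against a power figure the trial did not have. Second, the decision rule is left open. A favourable difference with a two-sided p-value between 0.05 and 0.10 meets the criterion in 15.1 and fails the one in 15.2. In an open-label trial, that choice should not wait until data have been seen.

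A smaller point concerns the effect-size scale. If the formula's denominator is read as the standard deviation of change on each side of the mouth, it is not the quantity in the table unless the two sides' changes correlate at exactly 0.5.

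**Working it through.** **Inputs (all from 15.1 unless noted)**

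- Effect size d = 0.5 (mean difference 0.5 in absolute value, standard deviation of differences 1.0).
- n = 27 completers; about 20% dropout; 34 recruited.
- Significance level 0.05, one-sided for the sample size; 0.05, two-tailed for the analysis (15.2).

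**Formula.** For a paired t-test, the statistic under the alternative follows a noncentral t distribution with n − 1 degrees of freedom and noncentrality d√n. One-sided power is the probability that it exceeds the 95th percentile of central t. Two-sided power is the probability that its absolute value exceeds the 97.5th percentile.

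**Step 1: reproduce the plan's figure.** At n = 27, the degrees of freedom are 26 and the noncentrality is 0.5 × √27 = 2.598.

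- One-sided critical value 1.706: power 81.2%.
- At n = 26, one-sided power is 79.8%.

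So 27 is the smallest n reaching 80% one-sided. For dropout, 27 / 0.8 = 33.75, rounded up to 34. Both figures in 15.1 are correct for a one-sided test.

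**Step 2: the test in 15.2.** With the same n and noncentrality, the two-sided critical value is 2.056.

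| Completers | One-sided 5% power | Two-sided 5% power |
|---|---|---|
| 26 | 79.8% | 68.8% |
| 27 | 81.2% | 70.6% |
| 33 | 87.8% | 79.5% |
| 34 | 88.7% | 80.8% |

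The type II error at n = 27 is 100% − 70.6% = 29.4%, against the stated 20%. A normal approximation gives 83.0% one-sided and 73.8% two-sided, so the gap is not an artefact of the exact method.

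**Step 3: what two-sided 80% power would require.**

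- At d = 0.5: 34 completers, hence 34 / 0.8 = 42.5, rounded up to 43 recruited.
- At 27 completers: solving for d gives 0.56.

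**Step 4: the effect-size denominator.** If SD is the standard deviation of change on each side and ρ the correlation between sides, the standard deviation of the differences is SD × √(2(1 − ρ)). The two are equal only when 2(1 − ρ) = 1, that is, ρ = 0.5. The documents give no ρ, so the values below are assumed. Taking 0.5 on the per-side scale, with n = 27 and two-sided 5%:

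| Assumed ρ | √(2(1 − ρ)) | Effect on the paired scale | Power |
|---|---|---|---|
| 0.3 | 1.183 | 0.423 | 56% |
| 0.5 | 1.000 | 0.500 | 71% |
| 0.7 | 0.775 | 0.645 | 90% |

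Step 2 uses the table's standard deviation of differences directly and does not depend on ρ.

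**The case against.** The best counter-argument is that 71% is conditional. Section 15.2 defines the ITT population as all enrolled patients who received at least one treatment, so up to 34 might be analysed, and visits at 4, 12 and 24 weeks mean that some dropouts could contribute earlier data. Two-sided power would be 75.4% with 30 analysed and 80.8% with 34. The condition is fair and should be attached to the figure. It does not rescue 15.1, which bases its claim on 27 completers, expects about 20% dropout and is accompanied by no stated method for missing data.

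It can also be said that nothing in 15.1 is miscalculated. That is true: the fault is the mismatch between two sections. Nor does the two-tailed test inflate type I error. But the stated power is still wrong for the test that will be run.

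A directional hypothesis could justify a one-sided test. Section 15.2 would then have to say so, and as written it rules this out.

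On the denominator, the footnote in 15.1 announces a common standard deviation and then supplies the standard deviation of differences. The authors may simply be using the first phrase loosely for the second. That is plausible, and it makes this a labelling point, secondary to the sidedness conflict.

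**Conclusion.** The concern holds. Section 15.1 sizes the trial for a one-sided 5% test, section 15.2 makes all tests two-tailed at 5%, and nothing in the documents reconciles them. With 27 completers and an effect size of 0.5, power under the planned analysis is about 71%, roughly 10 points below the 81.2% that the same n gives one-sided. This assumes a paired t-test, one paired difference per participant and the table's standard deviation of differences. If the signed rank test is used instead, power is slightly lower: about 68%, assuming normal data and a relative efficiency of 0.955, a figure not in the documents. The denominator wording is a genuine but minor inconsistency, and the 71% does not rest on it.

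**What to change.** Keep the two-tailed rule in 15.2 and restate the power in 15.1 along these lines:

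> With 27 completers, a paired t-test at two-sided 5% has 71% power for an effect size of 0.5 (mean difference 0.5 mm, standard deviation of differences 1.0 mm), or 80% power for an effect size of 0.56.

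Millimetres are the protocol's unit for pocket depth. Section 15.1 prints no unit beside these two numbers, so the sponsor should confirm it when making the change.

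Correct the sidedness and power rows of the table, and state the sidedness in the opening sentence of 15.1. Replace the formula's denominator with the standard deviation of the within-patient difference in change, test minus control, so that formula and table describe the same quantity.

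The cost is wording in 15.1 and a less favourable stated power; enrolment, data collection and analysis do not change. If the sponsor would rather keep 80% power for an effect size of 0.5, the alternative is 34 completers, or 43 recruited at 20% dropout, with the participant number in 5.4 changed to match.

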15.2. STATISTICAL METHODS

Study Population:

Intent-to-treat (ITT) population – all patients enrolled to the study who received at least one treatment.

Per Protocol (PP) population - all patients in the ITT population who completed the study according to the protocol and with no major protocol violations.

General

All measured variables and derived parameters will be listed individually and, if appropriate, tabulated by descriptive statistics. For categorical variables, summary tables will be provided giving sample size, absolute and relative frequency and 95% CI (Confidence Interval) for proportions by study arm. For continuous variables, summary tables will be provided giving sample size, arithmetic mean, standard deviation, median, minimum and maximum and 95% CI (Confidence Interval) by study arm for means of variables.

All tests will be two-tailed, and a p-value of 5% or less will be considered statistically significant.

The data will be analyzed using the SAS ® version 9.3 (SAS Institute, Cary North Carolina).

Periodontal pockets treated with Pocket-X Gel will be analyzed vs.control pockets.

Efficacy assessment

The following efficacy parameters will be summarized in appropriate tables by treatment and visit. Changes from baseline will be summarized as well.

- Pocket probing depth
- Bleeding index
- Recession level
- Clinical attachment level
- Mobility grade
- Furcation
- Specific periodontal bacteria quantification [optional]

The Paired T-test or Signed rank test for two means (paired observations) (as is appropriate) will be applied for analyzing the calculated changes by time point within each treatment.

The Paired T-test or Signed rank test for two means (paired observations) (as is appropriate) will be applied for analyzing the difference in the above measurements and changes between the treatments.

Responder will be defined based on improvement of gingival healing and natural sealing of periodontal pockets. Chi-square test or Fisher's Exact test (as is appropriate) will be applied for comparing the proportion of responders between the tested and the control segments.

The efficacy results will be compared also to literature data, if available. The two-sample T-test or Non-parametric Wilcoxon-Mann-Whitney Rank sum test for independent samples (as is appropriate) will be applied for comparative analysis.

Safety assessment

Safety assessments will be based on Adverse Events (AEs) and oral inspections recorded at each visit.

All AEs will be coded using coding dictionaries MedDRA (most updated version) and will be

summarized by system organ class (SOC) and preferred term (PT).

AEs will be listed individually including SOC, PT, seriousness of event, onset and resolution dates, duration, severity, relationship to the study treatment, action taken and outcome.

Frequency AEs and treatment-related adverse events will be summarized in tables by SOC, PT and treatment and by seriousness.

In case that the adverse event is localized, frequency of local AEs will be compared between the segment(s) treated with Pocket-X Geland the untreated segments of the same patient using Chi-square test or Fisher's Exact test (as is appropriate).

Adverse events will also be compared to adverse events reported during scaling and root planing studies, based on available literature. Chi-square test or Fisher's Exact test (as is appropriate) will be used for comparison in incidence of events.

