5. STUDY DESIGN

5.1. OVERALL DESIGN

This study is a single arm, open-label, split-mouth study.

All enrolled participants will initially undergo root planing and scaling on the entire mouth. Following the completion of scaling and root planing, each participant will have one/two of his/her mouth segments (quadrants) treated with Pocket-X Gel. The contralateral segment(s) of the Pocket-X Gel-treated segment(s) will serve as control.

The study hypothesis is that patients treated with Pocket-X Gel following scaling and root planing will exhibit better periodontal pocket healing on their treated segment(s) than their untreated segment(s) as well as compared to data available in the literature concerning the efficacy of scaling and root planing.

The total duration of the study for each participant will be 6-7 months. The study will include a total of 5-7 visits, depending on the number of scaling and root planing sessions required,

based on the severity of each participant's periodontal disease. Follow-up visits will occur 4, 12 and 24 weeks after completion of scaling and root planing and first application of the studied device. Detailed description of each visit is provided under section 5.5 – Visits and Follow-Ups.

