9. STUDY ASSESSMENTS

9.1. EFFICACY ASSESSMENT

The following measurements will be recorded during the study, and will be used to assess the efficacy of the intervention:

- Plaque index
- Pocket probing depth
- Bleeding index
- Recession level
- Clinical attachment level
- Mobility grade
- Furcation
- Specific periodontal bacteria quantification [optional]

The above measurements will be recorded at baseline and at follow-up visits for each participant. The values will be recorded separately for each periodontal pocket. .

Efficacy data from follow-up visits will be compared to the baseline values in order to obtain the efficacy results. The efficacy results will be compared between treated periodontal pockets and control periodontal pockets and to data obtained from available literature.

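### No primary measure, visit or testing order is named: 15.1 sizes on pocket depth, but 15.2 applies one 5% rule to six unranked measures

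*Combined protocol and SAP*

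**What the plan says.** **Efficacy tests (15.2).** Six measures are listed without rank: probing depth, bleeding, recession, attachment level, mobility and furcation. Bacterial counts are optional, and there is also a responder comparison. On reporting: "The following efficacy parameters will be summarized in appropriate tables by treatment and visit". A paired t-test or signed-rank test "will be applied for analyzing the calculated changes by time point within each treatment". In a separate sentence the same pair of tests "will be applied for analyzing the difference in the above measurements and changes between the treatments"; this sentence does not mention time points. The rule for significance is "All tests will be two-tailed, and a p-value of 5% or less will be considered statistically significant".

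**Sample size (15.1).** The rationale is "demonstrating a difference in change in pocket depth between the tested segments and the control". No visit is attached. The 27 participants are said to give "80% power to detect an effect size of 0.5 using a Paired t-test with a 0.05 one-sided significance level".

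**Unit of measurement and control.** Section 9.1: "The values will be recorded separately for each periodontal pocket". Section 5.1: "The contralateral segment(s) of the Pocket-X Gel-treated segment(s) will serve as control". Section 5.2 leaves two or three quadrants without gel, and 15.2 refers only to control pockets.

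**Objectives and hypothesis.** Section 4 speaks of measurements in general. The hypothesis in 3.3 gives pocket depth, bleeding and attachment level as examples in an open-ended list. Follow-up is at weeks 4, 12 and 24 (5.1, 5.5), with none marked as the main visit.

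**The concern.** The text reviewed does not identify the result that decides whether the gel works. If the measures or visits disagree, nothing in the plan settles which one counts. A reader of the report could not tell whether a significant finding was the one the study was built to test. With several unranked tests at the same threshold, the chance that at least one favours a gel with no effect is above that of a single test. The plan leaves open by how much, because even the number of between-treatment tests is unclear.

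The test sized in 15.1 also cannot be rebuilt from the plan. It needs one paired difference per participant, while readings are taken pocket by pocket and no rule for combining them is given.

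**Working it through.** **1. Where a primary test could be named**

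| Section | Measure singled out | Visit | Decides efficacy? |
|---|---|---|---|
| 3.3 hypothesis | none (open list) | none | no |
| 4 objectives | none | none | no |
| 5.1 design | none (pocket healing in general) | weeks 4, 12, 24, unranked | no |
| 9.1 assessments | none | baseline and follow-ups | no |
| 15.1 sample size | pocket depth | none | not stated |
| 15.2 methods | none (six unranked) | tables by visit | not stated |

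**2. The plan's own sample size**

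Inputs from 15.1: effect size 0.5, paired t-test, one-sided 0.05, n = 27. Power comes from the noncentral t distribution with n - 1 degrees of freedom and noncentrality 0.5 x sqrt(n). For n = 27 that is 26 degrees of freedom and 0.5 x sqrt(27) = 2.598.

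- One-sided 5%: power 81.2% at n = 27 and 79.8% at n = 26, so 27 reproduces. Recruitment: 27/0.8 = 33.75, so 34, which also reproduces.
- Two-sided 5%, as 15.2 requires (cut-off 2.056): power 70.6% at n = 27.
- Effect size for 80% two-sided power at n = 27: 0.56.
- Completers for 80% two-sided power at effect size 0.5: n = 33 gives 79.5% and n = 34 gives 80.8%, so 34. Recruitment: 34/0.8 = 42.5, so 43.

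**3. Chance of at least one false result in the gel's favour**

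The documents give no correlations, so these figures rest on assumptions. The gel is assumed to have no effect on any measure. One two-sided 5% test then favours it falsely 2.5% of the time. With k independent tests the chance is 1 - 0.975^k:

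- k = 3: 7.3%
- k = 6: 14.1%
- k = 18: 36.6%

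For correlated tests I simulated normal test statistics with a cut-off of 1.96, equal correlation between measures (0 to 0.8) and equal correlation between visits (0.5 to 0.8). Attachment level was modelled as pocket depth plus recession, so it is never independent of those two.

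| Reading of 15.2 | Visit correlation 0.5-0.8 | Upper end if visits uncorrelated |
|---|---|---|
| Pocket depth alone, three visits | 5-6% | 7% |
| Six measures, one visit | 6-13% | not applicable |
| Six measures, three visits | 12-29% | 33% |

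The lower ends are at the highest correlations and the upper ends at the lowest. Repeating the one-visit case as paired t-tests on 27 patients gave 7-13%. If the mobility and furcation grades never reach significance, the other four measures give 5-8% at one visit and 9-19% at three.

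The last row of the table assumes between-treatment tests at each visit. That is inferred from the by-visit tables; 15.2 says by time point only for the within-treatment tests. The responder test, the optional bacteria test and separate tests on raw values are not counted.

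**The case against.** **Pocket depth is primary by implication.** Section 15.1 sizes the study to demonstrate a difference in that measure, and most readers would take it as the lead. This stands, and it narrows the gap mainly to the visit, the aggregation of sites and the missing statement that this test decides. It does not close the gap: pocket depth at three unranked visits still gives 5-6% against 2.5%.

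**A small open-label device study may be exploratory.** No section reviewed says so, and 15.1 states power and a significance level for demonstrating a difference.

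**Stronger readings do not hold.** A reader might infer that the plan allows success to be claimed on any one significant result. No section says that; equally, none rules it out. A reader might also multiply out 18 independent tests and quote 37% in the gel's favour, or 1 - 0.95^18 = 60% in either direction. The documents do not support those figures. By-visit testing between treatments is not stated, attachment level depends on pocket depth and recession, and the changes at all three visits share one baseline. For that last reason, the 33% obtained with uncorrelated visits is also unlikely.

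**The power conflict is a separate matter.** This is fair: the missing primary test does not depend on it. It is included because naming a two-sided primary test requires restating the power for that test.

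**Conclusion.** The omission is real and should be corrected before data are seen. It is limited to the text reviewed, which lacks the opening pages and section 11. Within that text, pocket depth is the evident lead measure, but no visit, per-patient summary or decision rule goes with it, and no order of testing covers the other measures.

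The excess over 2.5% ranges from about 5-6% on the narrowest reading to 12-29% on the widest. Both ranges depend on assumed correlations, and the widest also on an inferred visit-by-visit analysis. They bound what the plan leaves open; they are not estimates of this trial's error rate.

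The power discrepancy rests only on the plan's own inputs: about 71% rather than 80% with 27 completers.

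**What to change.** Add to 15.2, in substance:

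> The primary endpoint is the within-patient difference, gel segment(s) minus contralateral control segment(s), in change in pocket probing depth from baseline to [one named visit]. Site values are averaged to one value per patient and condition, using the same sites at both visits. The difference is tested once, at two-sided 5%. The efficacy conclusion rests on this test. All other measures and visits are secondary and are reported with confidence intervals.

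The sponsor should confirm these choices before data are seen:

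- the visit (week 24 is suggested only because it is the last);
- the site threshold (inclusion criterion 4 says 5 mm or greater; criterion 5 and the calibration section use more than 5 mm);
- averaging over sites;
- the contralateral segment(s) as the only control;
- paired t-test or signed-rank test;
- two-sided testing;
- the analysis set, with its rule for missing values at the chosen visit.

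In 15.1, restate the power as about 71% two-sided with 27 completers at effect size 0.5, or 80% at effect size 0.56.

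The cost is wording, a less favourable stated power, and the loss of other measures and visits as a basis for the efficacy conclusion. The power gap already exists between 15.1 and 15.2; the change only makes it visible. More patients (34 completers, 43 recruited) would be needed only if the sponsor wants to keep 80% two-sided power at effect size 0.5.
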